CLINICAL TRIAL PROTOCOL

Protocol Title: The effect of dolutegravir on whole-body insulin sensitivity, lipid and endocrine profile in healthy volunteers

Protocol Number: CRF003

Version Version 4.0 20 Jan 2023

[figure not shown]
EudraCT No: 2020-004395-17

IRAS Number: 274870

Clinical Trial.gov: NCT04771754

Chief Investigator: [name]
St. Stephen's Centre
Chelsea and Westminster Hospital NHS Foundation Trust
[name]
[name]

Sponsor: Chelsea and Westminster Hospital NHS Foundation Trust
[name]
[name]

Protocol Approval: 
[name]

20 Jan 2023
dd mmm yyyy

GCP Compliance Statement:

This trial will be conducted in compliance with the protocol, the principles that have their origin in the Declaration of Helsinki and all applicable regulatory requirements

Synopsis

Name of Investigational Product:	Dolutegravir
Name of Active Ingredients:	Dolutegravir
Study Title:	The effect of dolutegravir on whole-body insulin sensitivity, lipid and endocrine profile in healthy volunteers
Phase of Study:	Phase I
Objectives:	
The objectives of this study are:
 
Primary
 
To quantify the difference in change in insulin sensitivity (determined by peripheral glucose uptake using a euglycaemic clamp) with the administration of dolutegravir (DTG) compared to no DTG for 28 days in HIV seronegative healthy volunteers.
 
Secondary
 
To investigate the effect of the dolutegravir on:
 
1. Adipocytokines by assessing adiponectin and leptin levels2. Ghrelin3. Pituitary hormones4. Lipid profile including lipid fractions5. Changes in indirect calorimetry6. Changes in food intake by food diaries7. Change in sleep parameters by sleep questionnaires8. Safety and tolerability of dolutegravir

Study Design	Randomised, crossover
Indication:	HIV negative volunteers
Methodology:	Insulin sensitivity determined by glucose disposal during steady state of euglycaemic clamp.
Planned Sample Size:	16
Summary of Eligibility Criteria:	
 • HIV negative subjects • Clinically well • BMI between 18 and 30kg/m² • Free from diabetes mellitus and metabolic syndrome • Not receiving any metabolically active medication or drugs likely to interact with antiretroviral therapy • Able and willing to provide informed consent
Number of Study Centres	One
Duration of Treatment:	28 days per sequence with washout between sequences

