Dose and Route of Administration:	Orally administered dolutegravir 50 mg once daily
Criteria for Evaluation:	Subjects will undergo three euglycaemic clamp procedures in order to determine the extent of glucose disposal. The first clamp will be performed prior to the commencement of the first study drug administration/no treatment, the second one following four weeks of study drug/no treatment, the third after the crossover phase to study drug/no treatment.
Primary Endpoint:	Change from baseline in total body glucose disposal by euglycaemic clamp method following 28 days treatment

Secondary Endpoints:

- Change from baseline in serum levels of fasting cholesterol fractions and triglycerides
- Changes from baseline in serum adipocytokines, ghrelin and pituitary hormones
- Changes from baseline in indirect calorimetry
- Caloric intake by food diaries
- Quality of sleep by sleep questionnaires
- Safety data including the number and severity of adverse events, as assessed by the medical dictionary for regulatory activities (MedDRA), from baseline to day 100

General Study Information

Name of sponsor:	Chelsea and Westminster Hospital NHS Foundation Trust [name]
Chief investigator:	[name] Chelsea and Westminster Hospital [name] [contact]
Co-Investigator	[name] Chelsea and Westminster Hospital [name] [contact]
Laboratory facilities: Biochemistry & Haematology	Imperial College NHS Foundation Trust Pathology Laboratory Chelsea and Westminster Hospital [name]
Virology & Hepatitis	Imperial College NHS Foundation Trust Dept. of Infection & Immunity [name] Charing Cross Hospital [name]

Medical expertise:	[name] & [name] Chelsea and Westminster Hospital [name] [contact]
Data management and Statistics:	Research and Development Office Chelsea and Westminster Hospital NHS Foundation Trust [name]
Monitor:	Research and Development Office Chelsea and Westminster Hospital NHS Foundation Trust [name] [contact] Email: [contact]

List of abbreviations and definitions of terms

ACTG	AIDS Clinical Trial Group
AE	Adverse event
AIDS	Acquired Immune Deficiency Syndrome
ALT	Alanine aminotransferase
AST	Aspartate aminotransferase
BMI	Body Mass Index
CM	Concomitant Medication
CRF	Case Report Form
DAIDS	Division of AIDS

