3.2 Study design

This is a 72-day (excluding screening period and follow up phone call) randomized study with two arms. The study will utilize a crossover design as described below.

Subjects will be randomised to start on dolutegravir 50 mg once daily OR no treatment for the first 28 day dosing phase of the study, then will cross over to the alternative for the second dosing phase, following a 2 week washout period (equivalent to 5+ dolutegravir elimination half-lives). Subjects will be contacted approximately seven days after the final euglycaemic clamp visit for a telephone follow up.

- **Day -28 to 0:** Screening
- **Day 1 (am):** Euglycaemic clamp 1
- **Day 1 (pm) to 28:** Dolutegravir (n=8)/Control (n=8)
- **Day 28 (am):** Euglycaemic clamp 2
- **Day 29 to 43:** Wash out (14 days)
- **Day 44 to 72:** Control (n=8)/Dolutegravir (n=8)
- **Day 72 (am):** Euglycaemic clamp 3
- **Day 100** Post study telephone contact

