5.1. Study Treatment Regimen

Group 1

Subjects will receive dolutegravir 50 mg once daily from day 1 for 28 days.

On the evening after the second clamp (day 28) they will cease treatment and will continue study activities for following 44 days.

Group 2

Subjects will receive no treatment from day 1 for 43 days on the day 44 they will initiate dolutegravir 50 mg once daily for 28 days (until day 72).

Dolutegravir will be dispensed by the Chelsea and Westminster NHS Trust pharmacy labelled as clinical trial supply.

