5.2 Treatment Compliance

Adherence to investigational product will be evaluated using pill counts of returned / unused investigational product. This assessment will be documented in the drug accountability record.

6. Visit schedule & Procedures

The schedule of assessments is summarised in Appendix 1.

Screening Visit

The screening visit should take place within 28 days prior to study day 1.

Subjects will be provided with written information about the study in the form of a subject information sheet and will be allowed adequate time for questions and to consider the study before agreeing to participate. It will be the responsibility of the investigator or co-investigator to obtain written informed consent prior to undertaking any procedures detailed in the protocol.

The investigator or designee must provide adequate explanation of the aims, methods, objectives and potential hazards of the study. It must also be explained to the subject that they are free to refuse or withdraw from the study for any reason without detriment to their future care or treatment.

The following information and procedures will be recorded and performed as part of the screening assessments:

- Written Informed Consent
- Medical and medication history, including smoking and substance history
- Demographics; gender, ethnic origin, age, height, weight, and body mass index (BMI)
- Vital signs: temperature, blood pressure, heart rate, respiration rate, oxygen saturation
- Physical examination including measurement of waist and hip size

- Haematology complete blood count (FBC) with differential and platelet count (haemoglobin, haematocrit, erythrocyte count, white blood count, differential white blood cell count, platelets)
- Pregnancy testing and last menstrual period (LMP) date in WOCBP subjects
- Biochemistry safety labs assessment for standard clinical chemistry (glucose, creatinine, sodium, potassium, calcium, aspartate aminotransferase, alanine aminotransferase, bilirubin, CRP), including HbA1c
- HIV antibody testing, hepatitis C (antibody) and B (surface antigen) screening
- ECG
- Urinary analysis (pH, specific gravity, leucocytes, nitrite, protein, glucose, ketones, urobilinogen, bilirubin, erythrocytes) and urine drug screen

Baseline

Subjects who meet all the inclusion and exclusion criteria and wish to take part in the study will be admitted to the unit on the morning of day 1. Subjects will remain in the unit for approximately four to six hours.

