The following study assessments will be performed (subjects must have fasted for at least eight hours):

- Adverse events
- Concomitant medication
- Vital signs (during the clamp procedure vital signs will occur every 30 minutes)
- Height/ weight/ BMI
- Measurement of waist and hip size
- Haematology: complete blood count (FBC) with differential and platelet count (haemoglobin, haematocrit, erythrocyte count, white blood count, differential white blood cell count, platelets)
- Biochemistry safety labs assessment for standard clinical chemistry (fasting glucose, creatinine, sodium, potassium, calcium, aspartate aminotransferase, alanine aminotransferase, bilirubin), including thyroid hormones (TSH, ft4), lipids (triglycerides, cholesterol, cholesterol HDL & LDL Sub-fractions) CRP and Hb1aC
- Urinary analysis (pH, specific gravity, leucocytes, nitrite, protein, glucose, ketones, urobilinogen, bilirubin, erythrocytes) and urine drug screen
- Pregnancy testing and LMP date in WOCBP subjects
- Adiponectin, leptin, ghrelin, testosterone
- Pituitary hormone function tests

- Dietary Questionnaire
- Sleep Questionnaires (PSQI)
- Euglycaemic clamp 1
- Insulin will be titrated 3 times during euglycaemic clamp procedure according to approved and verified formula sheet.
- ECG monitoring at 30 minute intervals during the clamp procedure
- Indirect calorimetry (all participants)

Prior to baseline visit subjects will be randomly assigned to Group 1 or Group 2:

Group 1:

- Dolutegravir 50 mg once daily for the first 28 days of the study.
- No treatment for the last 44 days of the study.

Subject will be dispensed study medication (Dolutegravir 50 mg) and instructed to self-administer the study drugs at home from the morning of day 2 until the morning prior to the next euglycaemic clamp day (Day 27).

Group 2:

- No treatment for the first 43 days of the study.
- Dolutegravir 50 mg once daily for the last 28 days of the study (day 44-72).

Subject will be dispensed study medication (Dolutegravir 50 mg) and instructed to self-administer the study drugs at home from the morning of day 45 until the morning prior to the next euglycaemic clamp day (Day 71).

Day 28

Subjects will be admitted to the unit in the morning and remain on the unit for approximately four to six hours. Group 1 subjects will take their last dose of study medication in the unit in the morning of the visit.

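### Dosing instructions conflict: Group 1's first dose is placed both before noon and after clamp 1 on Day 1, and Group 2's 28 days come to 29 doses

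*Combined protocol and SAP*

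**What the plan says.** **Group 1, first dose.** The synopsis (Criteria for Evaluation) states: "The first clamp will be performed prior to the commencement of the first study drug administration/no treatment". Section 3.2 agrees: clamp 1 is on Day 1 in the morning, and the line that starts treatment, "Dolutegravir (n=8)/Control (n=8"), is dated from the afternoon of Day 1. Section 5.1 gives no time of day: "Subjects will receive dolutegravir 50 mg once daily from day 1 for 28 days". Section 6 (Baseline) lists the fasting samples, clamp 1 and calorimetry, then has Group 1 dose at home from the morning of Day 2 to Day 27. It has no line for a dose on Day 1. The self-administered dosing row of the Appendix 1 flowchart has a tick at Baseline with a morning tag and the Group 1 footnote.

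**Group 2, duration.** The synopsis gives "28 days per sequence with washout between sequences". Section 3.3 and the Section 6 Baseline text both say "Dolutegravir 50 mg once daily for the last 28 days of the study (day 44-72"). Section 5.1 says that on Day 44 "they will initiate dolutegravir 50 mg once daily for 28 days (until day 72"). The Section 6 visit text has the first dose in the unit on the morning of Day 44, home doses from Day 45 to Day 71, and a last dose in the unit on the morning of Day 72.

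**Related text.** Section 3.2 labels Days 29 to 43 "Wash out (14 days"). Section 5.2 says: "Adherence to investigational product will be evaluated using pill counts of returned / unused investigational product".

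**The concern.** A baseline clamp and baseline fasting samples are meant to be drug-free. A flowchart entry that puts Group 1's first dose on that same morning leaves the order of dose and measurement open, and it does so in one sequence only. The Day 28, Day 44 and Day 72 visits each have an explicit sentence about dosing in the unit. Baseline does not, so staff looking for the Day 1 instruction would reasonably turn to the flowchart.

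This bears on the stated endpoints. The primary endpoint in Section 3.1 is a change from baseline with 28 days of dolutegravir, and Section 7.1 frames the sample size as Baseline against Week 4 under dolutegravir. Indirect calorimetry is the most exposed measure. It is taken in everyone at baseline, then on Day 28 in Group 1 only and Day 72 in Group 2 only, so every later value is on drug and there is no control-period value.

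The Group 2 count matters less. It makes the stated duration wrong by one day against the visit instructions, and it leaves the expected number of tablets for the Section 5.2 adherence check undefined.

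**Working it through.** **1. Group 1: the sources side by side**

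| Source | Clamp 1 | First dose, Group 1 |
|---|---|---|
| Synopsis | before first drug | after clamp 1 |
| Section 3.2 | Day 1, morning | Day 1, afternoon |
| Section 5.1 | not stated | Day 1, no time |
| Section 6, Baseline | Day 1 visit | no Day 1 line; home doses from Day 2 |
| Appendix 1 | Baseline visit | Baseline, morning |

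The flowchart uses the same morning tag for Group 2 at Day 44. There it matches a Section 6 instruction to take the dose in the unit that morning, so the tag is naturally read as the time of the dose. Read that way, the Baseline cell cannot be reconciled with Section 3.2.

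**2. Consequence if the dose came first.** Let B be the true baseline and d the effect of a single dose on the measurement. The documents give no value for d. Group 1's recorded baseline becomes B + d; Group 2's stays B.

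- Section 7.3 contrast, where both periods share one recorded baseline: (DTG − B − d) − (control − B − d) = DTG − control. The error cancels for subjects with both periods, and Section 7.2 requires all clamps for the evaluable cohort.
- Change from baseline under dolutegravir: DTG − (B + d) in Group 1 and DTG − B in Group 2. The error in the simple average over 16 subjects is −d × 8/16 = −d/2.
- Calorimetry: only B and DTG exist in each group, so the same −d/2 applies and nothing cancels it.

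Baselines affected: at most 8/16 = 50%, all in Group 1.

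**3. Group 2 dose count.** The stated figure is 28 days, once daily. Inclusive count = last − first + 1.

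- Day 44 in the unit: 1
- Days 45 to 71 at home: 71 − 45 + 1 = 27
- Day 72 in the unit: 1
- Total: 1 + 27 + 1 = **29**

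The figure of 28 can be reproduced in three ways:
- Elapsed days: 72 − 44 = 28.
- Dropping Day 72: 71 − 44 + 1 = 28. This is possible from Section 5.1 alone, but Section 6 has a dose on Day 72.
- Dropping Day 44: 72 − 45 + 1 = 28. Section 6 has a dose on Day 44.

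The phrase in Sections 3.3 and 6 also conflicts with itself. The last 28 days of a 72-day study start on Day 72 − 28 + 1 = 45, not Day 44.

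**4. Cross-checks**

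- Group 1 with a Day 1 dose: 1 + 26 (Days 2 to 27) + 1 (Day 28) = 28. Without a Day 1 dose: 27.
- Segments of the 72-day study: Group 1, 28 + 44 = 72. Group 2, 43 + 28 = 71, one day short.
- Counting conventions:

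| | Stated | Inclusive | Elapsed |
|---|---|---|---|
| Group 1, Days 1–28 | 28 | 28 | 27 |
| Group 2, Days 44–72 | 28 | 29 | 28 |
| Washout, Days 29–43 | 14 | 15 | 14 |

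Neither convention reproduces all three stated figures.

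**5. Size of the Group 2 discrepancy.** It is one dose: 1/29 = 3.4% of the doses instructed, or 1/28 = 3.6% of the stated duration. With Day 44 held fixed and clamp 3 moved by the two days that Section 6.1 allows, the count runs from 70 − 44 + 1 = 27 to 74 − 44 + 1 = 31.

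**The case against.** The strongest reply on Group 1 is that the intended order is clear. The synopsis and Section 3.2 both put clamp 1 before the first dose, Section 6 calls Appendix 1 a summary, and no passage tells staff to dose before the clamp. The tag might mark only the morning of the visit. A post-dose baseline is therefore a possible scenario rather than an instruction. That stands, and it is why the harm is stated as conditional. It does not correct the flowchart or supply the missing Baseline line. The 8 of 16 figure is simply Group 1's allocation, an upper limit on the number of baselines exposed and not an effect size.

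The absence of control-period calorimetry is a separate design matter. It is used here only to show why a baseline error would not cancel for that endpoint.

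On Group 2, morning of Day 44 to morning of Day 72 is 28 elapsed days, and the washout is 14 on the same basis. That explains each figure separately, but the same convention gives 27 for Group 1. The visit window does make one dose small beside the variation already allowed. However, a window covers departures from a nominal schedule and does not reconcile two nominal schedules.

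Finally, the protocol states no expected pill count or adherence threshold, and it records start and stop dates (Section 9.2) and quantities dispensed and returned (Section 11.5). Adherence could be worked out from each subject's actual dates, so the pill-count consequence is modest.

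**Conclusion.** The concern holds on both points.

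- **Group 1 (the more important).** The flowchart and the text disagree on whether the first dose falls before or after noon on Day 1, and Section 6 does not settle it. If the flowchart were followed and the dose preceded the measurements, up to 8 of 16 baselines would be post-dose. Little or no effect is expected on the Section 7.3 contrast, given a shared baseline and complete pairs. Simple average changes from baseline under dolutegravir, including calorimetry, would be off by half the single-dose effect, which the documents do not quantify.
- **Group 2.** The visit instructions give 29 doses against 28 stated. This is a one-dose difference with little analytical consequence.

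Two smaller slips belong to the same calendar. The washout labelled 14 days covers 15 calendar days. Section 5.1 has Group 1 stop on the evening after clamp 2, whereas Section 6 has the last dose that morning in the unit.

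The correction is worth making because it settles whether Group 1's baseline is drug-free. No view is taken on which schedule is right.

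**What to change.** Reconcile the synopsis, Sections 3.2, 3.3, 5.1 and 6, and Appendix 1 to a single calendar. Specifically:

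- Make the flowchart and text agree on the order of the first dose relative to clamp 1, the baseline samples and baseline calorimetry. Add the matching Day 1 line to the Section 6 Baseline visit.
- Make Group 2's stated duration, day range and visit-by-visit dosing lines give the same count. Align the washout label and the Section 5.1 wording on when Group 1 stops.
- State the dispensing quantity and expected pill count per group that follow from that calendar, for use in Section 5.2.

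Which schedule applies is for the sponsor and investigator to decide. The cost is a text and flowchart correction with matching dispensing and pill-count figures. No visits, procedures or subjects are added.

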6.1 Euglycaemic Clamp

Following completion of the procedures mentioned above on days 1, 28 and 72 a euglycaemic clamp study will be performed to determine the extent of total and non-oxidative glucose disposal. After an overnight fast of at least 8 hours, the subject will be admitted to the Clinical Research Facility. This procedure will take approximately 3 hours. A primed/ continuous intravenous infusion of insulin, through an intravenous cannula, will commence in the morning at

an infusion rate dictated by the verified formula sheet, maintaining a mid-physiological level of hyperinsulinaemia for 180 minutes. Whole blood glucose will be assayed from a separate intraveneous cannula every 5 minutes. A negative feedback formula will be used to adjust the rate of infusion of 20 % dextrose in order to maintain euglycaemia at 4.5 mmol.L⁻¹. Whole blood potassium and haematocrit is measured at 30 minute intervals during the clamp procedure with electrocardiographic monitoring half hourly in order to monitor for changes towards hypokalaemia.

At 180 min, the insulin and glucose infusion is stopped immediately, and the subject fed. A final blood sugar, potassium and haematocrit level, and vital signs check will be performed before the subject is discharged from the unit.

The visit window for the euglycaemic clamp is up to plus or minus two days. All other visits should be adjusted accordingly.

6.2 Indirect Calorimetry

Indirect calorimetry by ventilated hood expires gas analysis will be used to determine energy expenditure during the course of the visit. Indirect calorimetry is the method by which the type and rate of substrate utilization, and energy metabolism are estimated in vivo starting from gas exchange measurements (carbon dioxide production and oxygen consumption during rest and steady-state exercise). Indirect calorimetry with hood canopy and dilution pump will be performed. Duration of indirect calorimetry is 30-40 minutes.

7 Statistical Analysis

Statistical analysis will be carried out after all subjects complete the study. All patients who have at least one dose of the trial medication, whether withdrawn prematurely or not, will be included in the safety analysis.

All safety data and adverse events will be summarised.

7.1 Sample size

No formal power calculations have been performed however, based on a treatment study in HIV-negative healthy volunteers over 4 weeks therapy [2, 9-11]; a power calculation can be determined by using the change in insulin-mediated glucose uptake after four weeks of therapy as the primary end point.

The study with eight [5] subjects per sequence will achieve 80% power to show equivalency in insulin-mediated glucose disposal under DTG treatment between Baseline and Week 4, assuming a standard deviation of difference between baseline and week 4 is 1.4 mg/kg x min per microUnit/mL insulin [1], the insulin-mediated glucose disposal equivalence boundary will range between -1.1 mg/kg x min per microUnit/mL to 1.1 mg/kg x min per microUnit/mL.

The primary endpoint of this study is the change from baseline in insulin sensitivity by euglycaemic clamp method with 28 days treatment.

The secondary endpoints include:

- Change from baseline in serum levels of fasting cholesterol, triglycerides
- Changes from baseline in serum adipocytokines, ghrelin and pituitary hormones
- Changes from baseline in indirect calorimetry

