1.2 Rationale

In a retrospective analysis in the NA-ACCORD, 22% of those with normal BMI at the start of anti-retroviral therapy (ART) became overweight after 3 years of ART, and 18% of those overweight at baseline becoming obese [1]. And a recent retrospective analysis by Menard et al [6] on patients stopping dolutegravir (DTG) due to adverse effects in the clinical setting, found that 7% had done so due to weight gain. Norwood and colleagues [7] has reported significantly increased weight gain in those switching to an INSTI-based regimen from an efavirenz-based (Atripla) based regimen. This weight gain was greatest among patients switching to DTG/ABC/3TC [7]. The etiology of weight gain in patients with undetectable plasma HIV RNA who change to another regimen and remain suppressed is unclear. An abrupt reduction in insulin sensitivity could

promote storage of excess circulating glucose and lipids in adipose tissue, but this is was speculative until now, therefor we propose the study of insulin sensitivity to address the underlining reasons for weight change in patients receiving dolutegravir based therapy.

Other studies have used a range of ART for 28 days in healthy volunteers looking at similar metabolic, coagulation and inflammatory markers and pharmacokinetic [8-11]. Given DTG half-life we wished to establish steady state to adequately examine the effect of a drug on weight gain, lipids and neuroendocrine markers. 28 days of DTG is Centre for Disease Control (CDC) recommended post exposure prophylaxis (PEP), therefore this duration of dosing is widely used and recommended in HIV-negative individuals [12].

HYPOTHESIS: There is no difference in change in insulin resistance and multiple lipid parameters in healthy volunteers when treated with dolutegravir compared with baseline values.

2. Trial Objectives

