2.1 Primary Objective

To quantify the difference in change in insulin sensitivity (determined by peripheral glucose uptake using a euglycaemic clamp) with the administration of dolutegravir (DTG) compared to no DTG for 28 days in HIV-seronegative healthy volunteers.

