7.3 Statistical Methods

Baseline demographic characteristics will be summarized using the descriptive statistics by treatment arms. Where quantitative data are hyper geometrically distributed median with interquartile ranges will be presented while Gaussian normal data will be summarized using the mean and standard deviation while qualitative data will be summarized using number of subjects with percentages.

The primary efficacy endpoint will be evaluated using analysis of variance (ANOVA) or Analysis of covariance (ANCOVA) fitting models for the crossover experiment, including treatment, period, and sequence as fixed effects, and subject within sequence as a random effect in the model. Least square mean difference between dolutegravir and no treatment period will be obtained from the ANOVA, or ANCOVA adjusting for potential confounding factors and the associated two-sided 95% confidence intervals will be constructed. It will be concluded that dolutegravir has equivalent impact as no treatment on insulin-mediated glucose disposal if the 90% confidence interval for the mean difference between the two treatments is within $-1.1 \text{ mg/kg} \times \text{min}$ per microunit/mL to $1.1 \text{ mg/kg} \times \text{min}$ per microunit/mL boundary.

All data analyses will be performed using STATA statistical software (version 17). All p-values presented will be two tailed.

All patients who attend the baseline visit whether withdrawn prematurely or not will be included in the safety analysis. All safety data and adverse events will be summarised. Adverse events will be mapped using medical dictionary for regulatory activities (MedDRA) (the latest available version). The incidence of adverse event will be tabulated by system organ class, preferred term, and treatment. Additional summaries of adverse events will be displayed by highest grade, investigator's assessment of relationship to study drug, and effect on study drug discontinuation.

Statistical methods and power calculations for the study have been previously published by multiple different groups [3, 14-16].

Exploratory analyses will look at the effects of age, baseline BMI, sex and race on treatment effects.

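### Does the 80% power in section 7.1 belong to a different comparison from the one section 7.3 tests?

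*Combined protocol and SAP*

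**What the plan says.** Three places describe a change on dolutegravir relative to baseline.

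- The hypothesis in section 1.2: "There is no difference in change in insulin resistance and multiple lipid parameters in healthy volunteers when treated with dolutegravir compared with baseline values".
- The primary endpoint in section 3.1, which is the change in glucose disposal from baseline over 28 days of dolutegravir.
- The power statement in section 7.1, which says of a trial with eight people in each arm that it "will achieve 80% power to show equivalency in insulin-mediated glucose disposal under DTG treatment between Baseline and Week 4". The variability behind that figure is worded as "assuming a standard deviation of difference between baseline and week 4 is 1.4", and the equivalence boundary is ±1.1 in the same units.

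Two places describe a controlled comparison.

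- The primary objective in section 2.1 (and the synopsis) is the difference in change "with the administration of dolutegravir (DTG) compared to no DTG for 28 days in HIV-seronegative healthy volunteers".
- Section 7.3 fits a crossover model with treatment, period and sequence as fixed effects and subject within sequence as a random effect. It then states: "It will be concluded that dolutegravir has equivalent impact as no treatment on insulin-mediated glucose disposal if the 90% confidence interval" for the difference between the two treatments lies within ±1.1.

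The synopsis endpoint and the endpoint line in 7.1 ("The primary endpoint of this study is the change from baseline in insulin sensitivity by euglycaemic clamp method with 28 days treatment") do not name a drug and fit either reading.

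On sources, 7.1 opens with "No formal power calculations have been performed however", points to references 2 and 9 to 11 as the basis for a calculation, and attaches reference 1 to the value 1.4. Section 7.3 adds: "Statistical methods and power calculations for the study have been previously published by multiple different groups", citing references 3 and 14 to 16.

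**The concern.** A power figure is useful only if it refers to the quantity that will be tested. Here the 80% is attached to a before-after change on dolutegravir, which has no decision rule, while the rule in 7.3 applies to dolutegravir minus no treatment. The SD of that second difference is not given, and 7.1 does not say that 1.4 is assumed for it.

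If the before-after comparison were taken as primary, the trial would lose the protection of its crossover design. Any change between clamps unrelated to the drug would be counted as drug effect, or could hide one. The same data could then give two different answers.

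The source of 1.4 is also hard to trace. Section 1.2 and the reference list describe reference 1 as a retrospective cohort analysis of weight gain on antiretroviral therapy, an unlikely source for the SD of a clamp measurement. The disclaimer about formal power calculations sits awkwardly beside a stated 80%.

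**Working it through.** **Inputs.** N = 16, 8 per sequence (4.1, 7.1); SD of the within-subject difference 1.4 (7.1); margin ±1.1 (7.1, 7.3); 90% confidence interval, that is, two one-sided tests at 5% each (7.3); clamps on Days 1, 28 and 72 only (6.1). The true difference is not stated; 0 is assumed.

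**Step 1: reproduce the 80%.** For the 2×2 crossover, the standard error of the treatment difference is

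SE = (SD/2) × √(1/8 + 1/8) = 0.7 × 0.5 = 0.35, which equals 1.4/√16.

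With 14 degrees of freedom the one-sided 5% t value is 1.761, so at SD 1.4 the half-width of the 90% interval is 1.761 × 0.35 = 0.616. The observed difference must then lie within about ±(1.1 − 0.616) = ±0.484. Integrating over the sampling distribution of the variance estimate gives:

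| Total N | Power, df N−2 (crossover) | Power, df N−1 (paired) |
|---|---|---|
| 14 | 73.9% | 74.5% |
| 15 | 78.3% | 78.7% |
| 16 | 82.0% | 82.4% |

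Sixteen is the smallest balanced number reaching 80%. The arithmetic in 7.1 is right for a within-subject difference with SD 1.4 in 16 subjects.

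**Step 2: which difference is tested?** Write Y1, Y28 and Y72 for a subject's three clamp values.

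- Group 1: (Y28 − Y1) − (Y72 − Y1) = Y28 − Y72.
- Group 2: (Y72 − Y1) − (Y28 − Y1) = Y72 − Y28.

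Day 1 cancels. With a common variance σ² and a common correlation ρ among the three clamps,

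Var(Y28 − Y1) = 2σ²(1 − ρ) = Var(Y28 − Y72).

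Under that condition an SD of 1.4 for the change from baseline is also the SD of the treatment difference, and the 82% applies to the rule in 7.3.

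**Step 3: can 7.1 be meant literally?** Only Group 1 has a Day 1 to Day 28 change on dolutegravir. Group 2 reaches its dolutegravir clamp on Day 72, 71 days after Day 1. A paired test on Group 1 alone (n = 8, SD 1.4, df 7) has about 33% power. The literal wording cannot yield 80%; a within-subject difference in all 16 can. The arithmetic does not show which such difference was meant, but the count per sequence and the margin shared with 7.3 point to the crossover contrast.

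**Step 4: how much rests on 1.4?** The documents give no alternative, so these SDs of the treatment difference are assumed (N = 16, df 14, true difference 0):

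| SD | 1.2 | 1.4 | 1.5 | 1.6 | 1.8 |
|---|---|---|---|---|---|
| Power | 93% | 82% | 75% | 67% | 50% |

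Power equals 80% at SD 1.43. At SD 1.4, a true difference of 0.1, 0.2 or 0.5 gives 80.4%, 75.8% or 49.1%.

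**The case for a change.** The best case for amending the plan is that the mismatch is in plain words. Section 1.2 and the power sentence in 7.1 name only dolutegravir against baseline, and 2.1 and 7.3 name something else. Equal correlation among clamps is not guaranteed: Day 1 to Day 28 spans 27 days and Day 28 to Day 72 spans 44, so the later difference could be the more variable. The slack is thin, since the SD need only rise from 1.4 to about 1.43 for power to fall below 80%. The reference attached to 1.4 does not fit, and the edits would be cheap.

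Most of this stands as description. The wording is inconsistent, the equal-variance step is unstated, and reference 1 looks misplaced. The text is not without a basis, though: 7.1 also cites references 9 to 11, whose titles describe studies in healthy or HIV-seronegative volunteers, and a stray reference 5 beside the subject count suggests that the numbering slipped. Which source holds 1.4 cannot be checked from the documents. The disclaimer may itself be true if the figure was borrowed from published work.

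What does not stand is the step from loose wording to a risk for the conclusion. The two comparisons could disagree on the same data, but no section plans a before-after equivalence test. The endpoint in 3.1 can be read as the variable measured in each period, with the contrast supplied by the objective and the model.

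**Conclusion.** No change follows. An analyst who carries out section 7.3 as written obtains a controlled comparison with a fixed margin and rule, and it answers the objective in 2.1. The baseline wording in 1.2 and 7.1 is loose shorthand that sets no competing decision rule.

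The stated power is not shown to be wrong, and nothing here shows that 16 is too few. It is 82% for the tested contrast, given an SD of 1.4, a true difference of 0 and equal variances and correlations across the three clamps. The last condition is a reasonable gap-filler, but it is not written down.

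If the true SD is larger, the trial is less likely to show equivalence. The chance of wrongly declaring equivalence at the margin stays at 5%, because the interval in 7.3 uses the variability observed in the trial and not the planning value. Tidier wording and a corrected citation would help a reader check 7.1, but would leave the visits, the sample size, the analysis and the conclusion as they are.
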